11.3.5.3 Pulmonary safety

Descriptive summary statistics by visit and study treatment will be provided for observed treatment-emergent values and changes from baseline by visit in FEV₁ and FVC (all expressed in absolute change, % change and % of predicted value).

The number and proportion of treatment-emergent decreases of percent predicted FEV₁ or FVC > 20% from baseline at any time up to EOT + 30 will be summarized by treatment.

The trend effect of treatment of the percent predicted FEV₁ over time will be analyzed by treatment using a regression analysis with time as the independent variable and % predicted FEV₁ calculated with the age at the time of the assessment as the dependent variable. Assessments during up-titration and after the subject discontinues treatment will not be included in this analysis.

The mean (and 95% CIs), change and % change from baseline to EOS and from baseline to EOT in FEV₁ or FVC (absolute and % of predicted) will be plotted by treatment. A scatter plot will display the change from baseline to EOS versus the change from baseline to EOT on an individual subject level by study treatment.

For the subset of subjects with a decrease of > 200 mL or > 12% in FEV₁ or FVC from baseline at EOT, the number and percentage of subjects with a decrease of ≤ 200 mL and ≤ 12% from baseline to last available FU in FEV₁ or FVC will be summarized by treatment.

Pulmonary safety events will be summarized as categorical variables.

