	
Safety endpoints
 
• Treatment-emergent AEs, serious adverse events, AEs of special interest[#], major adverse cardiovascular events (MACE), and AEs leading to premature discontinuation of study treatment;• Treatment-emergent morphological ECG abnormalities (as defined by the ECG provider);• Change in 12-lead ECG variables (HR, PR, QRS, QT, QT corrected for HR on the basis of Bazett's formula [QTcB], QT corrected for heart rate on the basis of Fridericia's formula [QTcF]) from pre-dose to selected post-doses assessments (1 h, 2 h, 3 h, 4 h) on Day 1 and on day of re-initiation of study treatment when post-dose monitoring is required;• Notable abnormalities* for selected 12-lead ECG variables (HR, PR, QT, QTc) at 3-hour post dose assessment on Day 1, Week 12 and at the re-initiation of study treatment when post-dose monitoring is required;• Treatment-emergent decrease of FEV₁ or FVC > 20% from baseline values or decrease of percent predicted FEV₁ or FVC > 20 percentage points from baseline values;• Change in FEV₁ or FVC from baseline, absolute and % of absolute change to all timepoints up to EOS;• Change from baseline to EOS versus change from baseline to EOT in FEV₁ or FVC (absolute and % of predicted);• Among subjects with a decrease of > 200 mL or > 12% in FEV₁ or FVC from baseline to EOT, reversibility defined as a decrease of < 200 mL or < 12% in FEV₁ or FVC from baseline to last available post-EOT follow-up• Treatment-emergent notable blood pressure abnormalities*;• Treatment-emergent notable laboratory abnormalities*;• Change in body weight from baseline to EOS;• Treatment-emergent electronic Columbia-Suicide Severity Rating Scale (eC-SSRS) suicidal ideation score of 4 or above, or a "yes" response on the eC-SSRS suicidal behavior item.• Change in John Cunningham Virus serology from baseline up to EOS. 
[#] The selection of AEs of special interest is based on the anticipated risks of treatment with ponesimod and on the events that may be related to MS

--	---

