1.3.2.4 Safety and tolerability

Clinical studies to date have identified transient changes in heart rate (HR) and atrioventricular (AV) conduction as the most prominent safety-related signal with ponesimod. Oral doses of ponesimod resulted in dose-dependent sinus rate reductions in all treated subjects; the changes were transient and resolved largely within 6–10 hours after dosing. In some subjects, these HR reductions were accompanied by a transient effect on AV conduction with prolongation of the PR interval on the electrocardiogram (ECG) and, occasionally, second degree AV-block. The effects on HR and AV conduction diminish with repeated administration of ponesimod, indicating desensitization. To minimize the first-dose effects on HR and AV conduction, a dose up-titration regimen was successfully tested and is implemented in current clinical trials.

Breathing difficulties and pulmonary function test (PFT) changes have also been detected in humans. Mild transient dyspnea/cough was noted frequently 2–6 hours after an oral dose of 40 mg or higher, and was associated with a clinically relevant forced expiratory volume in 1 second (FEV₁) decrease from baseline. Symptoms resolved spontaneously upon discontinuation of treatment with ponesimod, and PFTs returned to baseline upon drug discontinuation. In study AC-058B201, dyspnea AEs were reported in 6.1% of patients in the ponesimod 20 mg group as compared to 3.3% in the placebo group. Accordingly 13.5% of patients in the ponesimod 20 mg group had FEV₁ < 80% of their baseline measurements at least once during the treatment period compared to 3.3% in the placebo group. However, none of the patients in the 20 mg group discontinued treatment due to a respiratory AE. Doses higher than 20 mg were associated with decreased tolerability; there were increased discontinuation rates with 40 mg mainly due to more pronounced pulmonary function effects and an increased incidence of liver enzyme elevations.

Data from an interim analysis of the long-term extension study AC-058B201/B202 with a cut-off date of 31 October 2014 showed that dose-dependent decrease in FEV₁ remained stable in patients treated with ponesimod for up to approximately 4 years and were reversible after treatment discontinuation.

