13. Type 1 or 2 diabetes which is poorly controlled according to investigator judgment or diabetes complicated with organ involvement such as diabetic nephropathy or retinopathy.

Pulmonary

14. Subjects with a clinically significant pulmonary condition including:

- Asthma which is insufficiently controlled according to investigator judgment, or any hospitalization due to asthma exacerbation within 6 months prior to randomization;
- Abnormal PFTs: FEV₁ or forced vital capacity (FVC) < 70% of the predicted normal value at Visit 2 (Baseline).

15. Active or latent TB, as assessed by CXR performed at Visit 1 (Screening) or within 90 days prior to Visit 1 (Screening), or IFN gamma release assay (QuantiFERON-TB-Gold[®]) at Visit 1 (Screening), except if there is documentation that the subject has received adequate treatment for latent TB infection or TB disease previously.

Hematology

16. Any of the following abnormal laboratory values at Visit 1 (Screening) or Visit 2 (Baseline):

- Hemoglobin (Hb) < 100 g/L
- White blood cells (WBC) count < $3.5 \times 10^9/L$ (< 3500/mm³)
- Neutrophil count < $1.5 \times 10^9/L$ (< 1500/mm³)
- Platelet count < $100 \times 10^9/L$ (< 100,000/mm³)

Hepatic

17. Known and documented moderate or severe hepatic impairment.

18. Any of the following abnormal laboratory values at Visit 1 (Screening) or Visit 2 (Baseline):

- ALT/SGPT > 3 × ULN
- AST/SGOT > 3 × ULN
- Total bilirubin > 1.5 × ULN (unless in the context of known Gilbert's Syndrome)

Other categories

19. Contraindications for MRI such as:

- Pacemaker, certain metallic implants such as artificial heart valves, aneurysm/vessel clips and any metallic material in high-risk areas which are contraindicated for MRI according to the local procedures;
- Severe renal insufficiency defined as a calculated creatinine clearance < 30 mL/min (Cockcroft-Gault);
- Claustrophobia if its nature or severity is prohibitive for performing MRI according to the investigator's judgment.

20. History of clinically significant drug or alcohol abuse.

21. Known allergy to any of the ponesimod formulation excipients.

22. Any other clinically relevant medical or surgical condition, which, in the opinion of the investigator, would put the subject at risk by participating in the study.

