6.2 Safety endpoints

The treatment-emergent period is defined as the time from first study drug intake up to 30 days (inclusive) after last study drug intake. The following safety endpoints will be analyzed:

- Treatment-emergent AEs, SAEs, AEs of special interest[#], MACE, and AEs leading to premature discontinuation of study treatment;
- Treatment-emergent morphological ECG abnormalities (as defined by the ECG provider);
- Change in 12-lead ECG variables (HR, PR, QRS, QT, QT corrected for HR on the basis of Bazett's formula [QTcB], Fridericia's formula [QTcF]) from pre-dose to selected post-dose assessments (1 h, 2 h, 3 h, 4 h) on Day 1 and on day of re-initiation of study treatment when post-dose monitoring is required;
- Notable abnormalities* for selected 12-lead ECG variables (HR, PR, QT, QTc) at 3-hour post-dose assessment on Day 1, Week 12 and at the re-initiation of study treatment when post-dose monitoring is required;
- Treatment-emergent decrease of FEV₁ or FVC $> 20\%$ from baseline values or decrease of percent predicted FEV₁ or FVC > 20 percentage points from baseline values;
- Change in FEV₁ or FVC from baseline, absolute and % of absolute change to all timepoints up to EOS;

- Change from baseline to EOS versus change from baseline to EOT in FEV₁ or FVC (absolute and % of predicted);
- Among subjects with a decrease of > 200 mL or > 12% in FEV₁ or FVC from baseline to EOT, reversibility defined as a decrease of < 200 mL or < 12% in FEV₁ or FVC from baseline to last available post EOT follow-up;
- Treatment-emergent notable blood pressure abnormalities*;
- Treatment-emergent notable laboratory abnormalities*;
- Change in body weight from baseline to EOS;
- Treatment-emergent electronic self-rated version of the Columbia-Suicide Severity Rating Scale (eC-SSRS) suicidal ideation score of 4 or above, or a “yes” response on the eC-SSRS suicidal behavior item;
- Change in JCV serology from baseline up to EOS.

[#] The selection of AEs of special interest is based on the anticipated risks of treatment with ponesimod and on the events that may be related to MS co-morbidities (e.g., seizures or stroke) as described in [Appendix 5](#); the final list of AEs of special interest will be defined in the Statistical Analysis Plan (SAP).

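### Section 11.3.5.3 counts a narrower lung-function event than the one defined in 6.2: one of its two limbs is lost, and which one depends on how its 20% is read

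*Protocol*

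**What the plan says.** Section 6.2 of the protocol lists the safety endpoints to be analysed. The lung-function event begins "Treatment-emergent decrease of FEV₁ or FVC" and sets a threshold of more than 20% from baseline for measured volume. It then adds, as an alternative, a "decrease of percent predicted FEV₁ or FVC > 20 percentage points from baseline". The synopsis gives the same two limbs. The units are deliberate: percent for measured volume, percentage points for percent predicted.

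Section 11.3.5.3 describes the analysis. The only threshold count of this kind there concerns percent predicted alone, for FEV1 and FVC, and the sentence that sets it up ends as follows: "or FVC > 20% from baseline at any time up to EOT + 30 will be summarized by treatment". Measured volume is not mentioned in that sentence, and the unit is a bare percent sign. The section closes with "Pulmonary safety events will be summarized as categorical variables", which does not say what such an event is.

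The time window is the same in both places, up to 30 days after the last dose.

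**The concern.** The endpoint and its analysis rule disagree within one document. Someone programming the table from 11.3.5.3 would not produce the endpoint of 6.2, and two programmers could produce different tables.

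Loss of pulmonary function is a recognised ponesimod effect. Section 1.5 lists it among the potential risks, and section 3.3 gives it as a main reason why 40 mg was less well tolerated. The earlier figures in section 1.3.2.4 are on the measured-volume scale, FEV1 below 80% of baseline at least once: "Accordingly 13.5% of patients in the ponesimod 20 mg group had" it, against 3.3% on placebo. If the bare percent sign is taken as points, the count loses direct comparability with that benchmark. If it is taken as relative change, comparability is largely kept, but subjects who qualify only through the percentage-point limb disappear.

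**Working it through.** **Threshold arithmetic.** Let B be baseline percent predicted.

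- A fall of 20 points is a relative loss of 20/B.
- A relative loss of 20% is a fall of 0.20 × B points.

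| B (% predicted) | Relative loss equal to 20 points | Points equal to a 20% relative loss |
|---|---|---|
| 70 (entry floor, exclusion 14 in section 4.4) | 20/70 = 28.6% | 14 |
| 80 | 25.0% | 16 |
| 100 | 20.0% | 20 |
| 120 | 16.7% | 24 |

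The limbs coincide only at B = 100. Below that the measured-volume limb is easier to meet; above it the percentage-point limb is.

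**Two subjects** (predicted value held fixed).

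- 80 to 62: 18 points, 18/80 = 22.5%. An event under 6.2; missed by 11.3.5.3 if read as points.
- 115 to 94: 21 points, 21/115 = 18.3%. An event under 6.2; missed by 11.3.5.3 if read as relative.

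**What each reading leaves.**

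- Points: 11.3.5.3 is exactly the second limb of 6.2; the first is lost.
- Relative: the predicted value nearly cancels, so 11.3.5.3 is close to the first limb; the second is lost. It is slightly stricter than the first limb because predicted values fall with age. If they fall by 0.5% to 1% a year (assumption), a 20% relative loss of percent predicted at 3 years is a volume loss of 1 − 0.8 × 0.985 = 21.2% to 1 − 0.8 × 0.97 = 22.4%.

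Either way the count is a subset of the 6.2 event.

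**Illustrative size.** From the protocol: 13.5% (ponesimod 20 mg) and 3.3% (placebo) for FEV1 below 80% of baseline, and the 70% entry floor. Assumed: baseline percent predicted normal, truncated at 70, with mean and SD (95, 12), (100, 13) or (105, 14); worst relative loss normal with SD s of 7 or 10 percentage points, independent of baseline. The mean loss is set to 20 − s × z(p), where z(p) is the upper-p normal quantile, so that the first limb occurs at the Phase 2 rate p. The point loss is the relative loss times B/100. FEV1 only. Simulated ponesimod results, in percent of subjects (shortfalls from unrounded values):

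| Baseline mean, SD | s | 6.2 event | Points only | Relative only | Shortfall, points reading | Shortfall, relative reading |
|---|---|---|---|---|---|---|
| 95, 12 | 7 | 15.3 | 11.5 | 13.5 | 3.8 | 1.8 |
| 95, 12 | 10 | 14.7 | 11.7 | 13.5 | 3.0 | 1.2 |
| 100, 13 | 7 | 16.9 | 14.3 | 13.5 | 2.6 | 3.4 |
| 100, 13 | 10 | 15.7 | 13.7 | 13.5 | 2.0 | 2.2 |
| 105, 14 | 7 | 19.0 | 17.2 | 13.5 | 1.7 | 5.5 |
| 105, 14 | 10 | 17.1 | 15.8 | 13.5 | 1.3 | 3.6 |

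On placebo the 6.2 event comes to roughly 4% to 6%. Widening the grid to baseline means of 90 to 105 with SD 12 and s from 6 to 10 stretches the ponesimod shortfall to 1.1 to 5.8 (points) and 0.6 to 6.0 (relative).

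**The case against.** Several points on the other side stand.

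- A reader might infer that 11.3.5.3 simply drops the measured-volume limb. That holds only if the percent sign means points. On a relative reading that limb is essentially kept and the other is lost. The sentence does not say which is meant.
- A reader might infer that the trial report will omit part of the endpoint. The protocol does not show that. Section 6.2 says its listed endpoints will be analysed, 11.3.5.3 promises a categorical summary of pulmonary events, and derivations are left to an analysis plan that is not at hand. What is shown is a contradiction between two sections.
- A reader might quote 1 to 5.5 points as one range. It pools two incompatible readings; the 5.5 arises only on the relative reading, where the volume limb is retained. The anchor rates come from a 24-week study, whereas treatment here runs 60 to 156 weeks on its own spirometry schedule.
- The between-arm contrast moves less than the ponesimod rate, because placebo counts fall too: 10.2 points (relative) or 8.6 to 12.2 (points), against about 11 to 13.4 for the 6.2 event.
- The signal is not hidden. Section 11.3.5.3 also reports FEV1 and FVC by visit as absolute change, percent change and percent predicted.

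None of this reconciles the two sections. The closing sentence of 11.3.5.3 defines no event. By-visit summaries do not give the proportion of subjects who ever cross a threshold. In 6.2 the items whose final definition is deferred to the analysis plan carry a footnote mark; this endpoint carries none, so its thresholds are fixed in the protocol and an analysis-plan author would inherit two conflicting rules.

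**Conclusion.** The inconsistency is real and the text settles it: no reading of the count in 11.3.5.3 reproduces the endpoint in 6.2 and the synopsis. The direction is certain on the points reading, where the count is one limb of a union; on the relative reading it needs only that predicted values do not rise over follow-up. The size is not certain. Roughly 1 to 4 percentage points of ponesimod subjects (points reading) or 1 to 5.5 (relative reading) rests on assumed baseline and change distributions, on rates from a shorter study and on FEV1 alone, so it illustrates and does not forecast.

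The consequence is limited to one descriptive safety proportion for a recognised drug effect. It does not touch alpha, power, sample size or any efficacy conclusion, and the documents do not show that the final report would be incomplete. It should be corrected, at modest priority.

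**What to change.** In 11.3.5.3, replace the single-limb count with the 6.2 event: the number and proportion of subjects who, from first dose to 30 days after the end of treatment, have either a fall from baseline of more than 20% in measured FEV1 or FVC, or a fall from baseline of more than 20 percentage points in percent predicted FEV1 or FVC. Name subjects as the unit; the present sentence refers to the number and proportion of decreases.

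Showing each limb next to the union is optional, since 6.2 does not ask for it, but it would give a row on the same scale as the Phase 2 figures.

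The cost is one sentence and, if the limbs are shown, two table rows. The spirometry is already collected. The reported proportion may be somewhat higher in both arms than under the present wording.

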11.3.5.4 Vital signs

Descriptive summary statistics by visit and study treatment will be provided for observed treatment-emergent values and absolute changes from baseline in HR, BP and body weight.

Treatment-emergent notable BP abnormalities will also be summarized descriptively. The definition for notable abnormalities is provided in [Appendix 6](#).

11.3.5.5 Laboratory endpoints

11.3.5.5.1 Laboratory tests

Descriptive summary statistics by visit and study treatment will be provided for observed treatment-emergent values and absolute and percentage changes from baseline for laboratory tests (hematology, blood chemistry, urinalysis). Data will be displayed in SI units whenever possible and graphical approaches will be applied for certain variables.

The lymphocyte count reversibility after EOT will be summarized by plotting the mean (and 95% CIs) change from baseline to EOT and change from baseline to EOS by treatment. A scatter plot will display the change from baseline to EOS versus the change from baseline to EOT on an individual subject level by study treatment.

Change in JCV serology from baseline up to EOS will be summarized descriptively.

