3.5.3.2 Post-treatment observation period

Subjects who prematurely discontinue study drug and complete the 30-day safety follow-up including the FU visit, will enter the PTOP which lasts until 60 weeks after randomization of the last subject or until Week 156, whichever is first (i.e., planned EOT visit) irrespective of treatment completion. It consists of an abbreviated schedule of assessments at the time of the originally scheduled 12-weekly visits. The aim is to

follow-up with the subjects after discontinuation of study treatment and to collect long-term data while the subject possibly receives other approved MS therapies.

While participating in the PTOP, subjects may not be enrolled in another clinical trial. They may, however, withdraw their consent to participate to this study at any time [see Section 9.2].

3.5.3.3 *End-of-Study*

[figure not shown]
The study level EOS will occur after all subjects have completed the safety FU period or the last visit of the PTOP.

For an individual subject, EOS is reached when treatment, post-treatment safety FU, and if applicable, the PTOPs have been completed:

- For subjects who complete the treatment period, and for subjects who prematurely discontinue study treatment and do not enter the PTOP, the EOS visit corresponds to the 30-day FU visit (FU).
- For subjects who prematurely discontinue study treatment and enter the PTOP period, the EOS visit corresponds to the last visit of the PTOP.

The overall study design is shown in [Figure 1](#).

Figure 1 AC-058B302 study design

D = day; DMF = dimethyl fumarate; EOS = End-of-Study; EOT = End-of-Treatment; FU = follow-up; V = visit; W = week; *Lymphocyte tests every 4 weeks (\pm 3 days) until Week 24; ** Subjects participating in the lymphocyte subset sub-study will have an additional FU visit approximately 7 days after the last dose of study drug (FU7d).

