8.3.1.2 Visit 20 – FU

If a temporary interruption of study treatment lasts more than 30 days and leads to permanent premature discontinuation, Visit 20 (FU) can be combined with the EOT visit.

The FU visit will take place at least 30 days after the last dose of study treatment, but no later than 37 days after last dose of study treatment. The visit includes:

- EDSS/FS.
- MS Relapse.
- FSIQ-RMS. At Visit 20 (FU), the FSIQ-RMS will be completed at home prior to the visit, ideally, during the 7 consecutive days preceding the visit.
- Recording of changes in concomitant medications.
- Body temperature.
- SBP/DBP.
- 12-lead ECG.
- Ophthalmological examination.
- Spirometry.
- Urinalysis.
- Hematology (including lymphocytes*), blood chemistry.
- PK sampling.

- Lymphocyte subsets (only at sites participating in sub-study).
- Serum pregnancy test for WOCBP.
- Recording of AEs and SAEs.

* If a total lymphocyte count $< 0.5 \times 10^9/L$ is observed at FU, an alert will be sent to the principal investigator and the sponsor [see Section 7.3.13.1]. Discontinuation of DMF treatment should be considered in accordance with prescribing information [Tecfidera USPI, Tecfidera SmPC].

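### The lymphocyte and lung-function displays compare EOT with EOS, which for early stoppers followed in the PTOP mixes ponesimod washout with later treatment; Visit 20 (FU) is the cleaner anchor

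*Protocol*

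**What the plan says.** - **Lymphocytes.** Section 11.3.5.5.1 states: "The lymphocyte count reversibility after EOT will be summarized by plotting the mean (and 95% CIs) change from baseline to EOT". The sentence goes on to name EOS as the other time point, the full pair being "plotting the mean (and 95% CIs) change from baseline to EOT and change from baseline to EOS by treatment", and a subject-level scatter plot of the two changes is added.
- **Lung function, plots.** Section 11.3.5.3 uses the same pair for the mean plots of FEV1 and FVC and adds: "A scatter plot will display the change from baseline to EOS versus the change from baseline to EOT on an individual subject level". Section 6.2 lists this contrast as a safety endpoint.
- **Lung function, threshold criterion.** Among subjects with a marked fall at EOT, Section 6.2 judges reversibility "from baseline to last available post EOT follow-up". Section 11.3.5.3 refers instead to the last available FU, and FU is elsewhere the name of Visit 20.
- **EOS.** Under Sections 3.5.3.3 and 9.1, EOS is the 30-day follow-up visit for completers and for early stoppers who do not enter the PTOP. For early stoppers who do enter it, EOS is the last PTOP visit.
- **PTOP.** Section 3.5.3.2 lets it run to the planned end of treatment, at most Week 156, to collect "long-term data while the subject possibly receives other approved MS therapies". Section 5.2.6 lifts the list of forbidden therapies for these subjects.
- **Visit 20.** Section 8.3.1.2: "The FU visit will take place at least 30 days after the last dose of study treatment, but no later than 37 days". Hematology and spirometry are both done there.
- **Safety window.** Section 6.2: "The treatment-emergent period is defined as the time from first study drug intake up to 30 days (inclusive) after last study drug intake". Section 11.3.5 makes this the default for safety tables and figures.

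**The concern.** A reversibility display should show whether a drug effect goes away once the drug is stopped. For that, the second measurement should be taken at a similar time off drug in everyone and before other treatment intervenes. EOS does this for completers. It does not do so for early stoppers in the PTOP, whose EOS value may come years later and after a change of MS therapy. Pooled by treatment arm, the second point of the plot is then a mixture. An incomplete return to baseline could come from the study drug or from a later one, and an apparently full return could come from stopping DMF.

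**Working it through.** **1. The plan's own timeline.** Section 3.5.4 gives a maximum participation of about 167 weeks from 45 days, 156 weeks and 30 days. Check: 45/7 + 156 + 30/7 = 6.4 + 156 + 4.3 = 166.7 weeks, which agrees.

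**2. Time off drug at EOS.** For a completer it is 30 to 37 days. For an early stopper who stays in the PTOP to its end:

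gap = planned end (Week 60 to Week 156) − week of last dose

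| Last dose | Planned end Week 60 | Planned end Week 156 |
|---|---|---|
| Week 4 | 56 weeks | 152 weeks (152 × 7/365.25 = 2.9 years) |
| Week 24 | 36 weeks | 132 weeks (2.5 years) |
| Week 48 | 12 weeks | 108 weeks (2.1 years) |

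**3. How many subjects this could touch (illustration only).** The protocol gives no discontinuation rate. The assumptions are:
- uniform randomisation over 104 − 45/7 = 97.6 weeks;
- a constant discontinuation hazard;
- every early stopper enters the PTOP and stays to its end.

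A simulation on this basis gives a mean planned treatment time of 108.8 weeks (2.1 years), in line with the protocol's approximate 2 years, and:

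| Assumed discontinuation | All subjects with EOS after day 37 | Median gap, early stoppers | Early stoppers off drug > 1 year at EOS |
|---|---|---|---|
| 10% | 10% | 55 weeks | 53% |
| 20% | 19% | 57 weeks | 55% |
| 30% | 29% | 59 weeks | 56% |

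**4. What can change in the gap.** Under Section 3.5.2.1, a subject who leaves treatment after a confirmed relapse or 24-week CDA also stops DMF and starts another approved therapy. Two statements in the protocol pull the count in opposite directions:
- Down: fingolimod is among the approved oral drugs (Section 1.1.4.2), and Section 1.2 says that S1P1 receptor modulators reduce peripheral lymphocyte counts.
- Up: Section 3.4.1 says that counts rise slowly over several weeks once DMF is stopped, while baseline was measured on DMF.

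The net sign depends on the mix of subjects, which the protocol does not give.

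**5. When recovery is expected.** Section 1.3.2.2 reports a return to baseline counts within one week of stopping ponesimod in Phase 2. Section 3.4.1 expects recovery within the 30-day follow-up, before the PTOP begins, and rests its argument against unblinding in the PTOP on that. For PTOP subjects the planned display does not look at that time.

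**6. The lung threshold criterion.** On the Section 6.2 wording, the last value after EOT for a PTOP subject will normally be the last PTOP spirometry, so the same problem arises. On the Section 11.3.5.3 wording, FU can be read as Visit 20, where it does not. The two sections need one time point.

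**The case against.** The strongest reply is that these are descriptive figures, that the follow-up data survive elsewhere, and that presentation details belong to the SAP. Much of this stands. No hypothesis test, sample size or treatment rule depends on the plots. Section 6.5.2 lists lymphocyte change by visit up to EOS, and Section 6.2 lists FEV1/FVC change at all time points up to EOS. The scatter plots are at subject level, and the placebo arm also has PTOP subjects. What remains is that the protocol itself names EOS as the second time point. The placebo arm is a fair reference only if early stopping and follow-on therapy are alike in both arms, which nothing ensures.

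Three stronger readings are tempting, and the documents do not support them.

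- *Lung-function reversibility as a whole is judged at EOS.* The plots use EOS, but Section 11.3.5.3 does not call them reversibility displays, and the threshold criterion is not labelled EOS in either section.
- *Most FU values drop out because the treatment-emergent window closes at day 30.* The by-visit laboratory summaries are indeed limited to treatment-emergent values, so days 31 to 37 fall outside them. But day 30 is inside, no distribution of visit days is given, the limit applies only where nothing else is stated, and the two endpoints above run to EOS.
- *The arm mean is shifted down by a known amount.* One could assume 20% of an arm in the PTOP, half of them on a drug that lowers counts by 50%, and obtain 0.20 × 0.5 × 50 = 5 percentage points. None of the three inputs is in the protocol, and the sum ignores the rise after stopping DMF.

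Visit 20 is not a perfect anchor either. Sections 8.2.10 and 8.3.1.2 let it be combined with EOT after an interruption of more than 30 days. A new therapy may start before it. Subjects who withdraw consent contribute no later data (Section 9.2).

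**Conclusion.** The point holds for early stoppers who enter the PTOP, and only for them. Their second measurement may fall up to about 150 weeks after the last dose, against 30 to 37 days for everyone else, possibly under another MS therapy and without DMF. For these subjects the lymphocyte display and the FEV1/FVC plots cannot separate ponesimod washout from later treatment. The threshold criterion has the same weakness on the Section 6.2 wording. The time gap follows from the protocol's own schedule. The share of subjects affected rests on the assumptions listed in the working, and neither the size nor the direction of the bias can be derived. Since the displays are descriptive and by-visit data up to EOS remain available, the severity is minor to moderate.

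**What to change.** 1. Base the lymphocyte reversibility display, the FEV1/FVC plots and the FEV1/FVC threshold criterion on Visit 20 against EOT, and state that Visit 20 values through day 37 are included even though the treatment-emergent window ends at day 30.
2. Where Visit 20 was combined with EOT after an interruption of more than 30 days, both values are off drug. Use the last on-treatment value as comparator, or show these subjects separately.
3. Flag subjects who started another MS therapy or stopped DMF before Visit 20. Both can be derived from the concomitant-medication form and the DMF log (Sections 5.2.2.1 and 5.2.3).
4. Show PTOP and EOS values in a separate display, split by that same status, and report how many subjects have no Visit 20 value.
5. Give the threshold criterion one time point in Sections 6.2 and 11.3.5.3. The two sections also join the volume and percentage limits differently (with or in one, with and in the other), which can be settled in the same edit.

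The cost is wording in the protocol or SAP and some programming. Hematology and spirometry are already scheduled at Visit 20, so no new assessment is needed, and sample size and power are unaffected.
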